5 PARTICIPANT RECRUITMENT AND CONSENT

5.1 Risks and Benefits to Participants

This is a double-masked, placebo-controlled RCT evaluating the efficacy and safety of ciprofloxacin (CIPRO®) and tamsulosin hydrochloride (FLOMAX®) in participants with CP. After evaluation of previous study data and physician participant records using these drugs, it is anticipated that there may be a direct benefit to the participants, however, direct benefits are not guaranteed. The information gained from this study may eventually prove beneficial to the treatment and diagnosis of other CP participants. Potential risks to the participants are limited to risks related to venipuncture and the use of the study drugs.

5.2 Risks of Ciprofloxacin (CIPRO®)

Ciprofloxacin is a synthetic fluoroquinolone antimicrobial agent with a broad spectrum of activity against aerobic bacterial organisms. The principal risks of ciprofloxacin use are as follows:

- Hypersensitivity to ciprofloxacin can occur. This can result in skin rashes or even severe anaphylactic reactions even after a single dose. Such severe reactions are very rare but participants should discontinue the drug if a skin rash or any other evidence of sensitivity to the drug occurs.
- Pseudomembranous colitis can occur after treatment with ciprofloxacin, as with most antimicrobial agents. This can result in severe diarrhea due to overgrowth of *Clostridium difficile* in the colon because of the removal of normal bacterial flora by ciprofloxacin. Participants should contact their physician if persistent diarrhea occurs after taking the drug.

- Ciprofloxacin can cause hypersensitivity to sunlight. Participants should avoid excessive exposure to sunlight or ultraviolet light while taking the drug. The drug should be discontinued if phototoxicity, such as sunburn, occurs.
- Central nervous system effects can occur with ciprofloxacin, including lightheadedness, dizziness, nervousness, anxiety, agitation, insomnia, nightmares or paranoia. Rarely, seizures or convulsions have been reported in participants taking ciprofloxacin. A history of seizure disorder should be reported to the physician prior to instituting therapy with ciprofloxacin.
- Ciprofloxacin may increase the effect of caffeine or the drug theophylline, used for asthma. Caffeine should be used with caution in the participant taking ciprofloxacin and the concomitant use of theophylline and ciprofloxacin may require dosage modification of theophylline.
- Rarely, participants taking ciprofloxacin have developed problems with tendons, including rupture or spontaneous tendon injury. Participants taking ciprofloxacin should discontinue the drug at the first sign of inflammation, pain or rupture of a tendon. If this occurs they should also rest, refrain from exercise and report the event to their physician immediately.

5.3 Risks of Tamsulosin (FLOMAX®)

Tamsulosin is a synthetic antagonist of the α_{1a} adrenergic receptor in humans.

- Hypersensitivity to tamsulosin can occur. This can result in skin rashes, pruritis, urticaria or angioedema. Participants with a known hypersensitivity to tamsulosin or any component of the drug formulation should be excluded.
- The principal risk of alpha adrenergic blockers is a lowering of blood pressure while on the drug. This can result in dizziness, syncope or postural hypotension. In the U.S studies of tamsulosin, symptomatic postural hypotension occurred in 1 of 502 men receiving 0.4 mg/day (0.4%) compared to none of 493 men receiving placebo. Participants should be warned of the risk of dizziness, lightheadedness or syncope when taking tamsulosin.
- Ejaculation abnormalities are associated with the use of tamsulosin. These include anejaculation, retrograde ejaculation or decrease in ejaculate volume. This was reported in 8.4% of men receiving 0.4 mg/day tamsulosin and 0.2% of men receiving placebo. In rare cases (less than 1 in 50,000) tamsulosin has been associated with priapism.
- Cimetidine can increase the level of tamsulosin. There are no other reported significant drug interactions.

5.4 Participant Recruitment

Participant recruitment will be conducted through the urology clinic at each of the participating Clinical Research Centers (CRCs). Participants referred to the CRCs with symptoms suggestive of CP/CPPS will be introduced to the RCT by the Research Coordinator and by a participant recruitment brochure describing the study (**See Appendix G**). In addition, a participant recruitment video, which also describes the study and participation requirements, has been developed for use by the ten participating clinical centers (**See Appendix H**). In an effort to

recruit minority participants, network clinical centers will seek the participation of primary care physicians, clinic centers, and other referral sources not previously included in the CPCRN. Potentially eligible participants will then be asked whether they are interested in participating in the study. The study will identify participants by referral source and zip code in order to more fully describe the study population.

5.5 Participant Selection

Initially every potential study participant will undergo a series of screening procedures that take approximately 2 - 3 weeks to complete. The screening phase entails at least two clinic visits. The screening process may take three visits, depending on procedure completion. The data collected and diagnostic procedures completed during this phase are identified in Sections 7.2 and 7.3, in the order in which they will be obtained or undergone. The order of the procedures has been selected to ensure that eligibility criteria checked by non-invasive methods precede those checked by more invasive methods, and to provide a balance of participant comfort and timeliness.

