7.2 Screening Visit #1

The first screening visit should occur no more than three (3) weeks and no less than one (1) week prior to randomization. During this screening visit, the forms and procedures listed below will be completed. If a participant fails to meet any of the study eligibility criteria, based on the data collected during this visit, he would not be required to complete the physical examination, urinalysis, or urine culture for the purposes of the study. (See **Appendix C**).

1. *Eligibility Criteria.*

Each participant will complete a preliminary screening form that checks whether he meets the initial inclusion/exclusion/deferral criteria. (These criteria will be verified at the second baseline visit.)

2. *Participant Contact Information.*

Participants will be asked to provide the clinical center with their address, phone number, primary care physician, and the name and address of two other contacts. This information will be stored at the CRC and available only to selected study personnel. Participants who have previously enrolled in the CPC will be asked only to update the previous information.

3. *Participant Medical History.*

Each participant will provide the research staff with his general medical history and specific genitourinary medical history. In particular, the participant will be asked to provide information regarding his disease and surgical histories.

4. *Participant Symptom Index.*

[figure not shown]
Each participant will provide the research staff with an assessment of his discomfort/pain by completing the full NIH-CPSI.

5. *Physical Examination.*

Each participant will undergo a focused physical examination. This examination will include an abdominal exam, external genital exam, rectal exam, prostate exam, and perineal exam. Participants enrolled in the CPC who have completed a physical examination within one (1) month of enrolling in the RCT, will not be asked to complete another physical examination.

6. *Urinalysis, Urine and EPS Specimens for Microscopy and Culture.*

Each participant will provide the research staff with three (3) urine specimens and an EPS (expressed prostatic secretion) specimen for analysis and culture. The urine specimen will be collected via the classic “four-glass test” (FGT) described in Meares and Stamey(28). The FGT will be attempted one time only at each of Screening Visit #1 and at the six (6) week clinic visit.

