The results from the EPS culture and the post-EPS urine (VB₃), if available, will be compared with the findings from the 1st voided urine (VB₁) and the midstream urine (bladder specimen or (VB₂)). A macroscopic urinalysis will be completed to quantify hemoglobin, protein, and glucose levels, and a microscopic urinalysis will be completed to quantify white blood cells, red blood cells and yeast. All specimens will be cultured for 5

days. The VB₂ culture will also be used to determine UTI status. Although the urinalysis will be performed at the respective CRC, all centers will be required to use the same brand of dipstick. In addition, a portion of the first voided specimen will be tested for chlamydia trachomatis using PCR. (**Appendix F**).

7. Next Visit Preparation.

- i. Appointment scheduling. An appointment will be made for Screening Visit #2, to occur no sooner than one (1) week and no later than three (3) weeks after Screening Visit #1.
- ii. Concomitant medications. Each participant will receive instructions from the RC to bring to Screening Visit #2 all/or a list of all the over-the-counter and prescribed medications that he is currently taking.
- iii. 1-day Voiding Log Supplies and Directions. Each participant will be provided with a voiding log. The participant will be asked to select a typical day, record the date, time and amount of each urination during a complete 24 hour time period. The participant will be asked to return the completed log at Screening Visit #2.

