1. NIH-CPSI
2. MOS-SF12
3. Follow-Up Symptoms
4. Follow-Up Contact
5. Adverse Events/Serious Adverse Events
6. Voiding Log
7. Medication Diary
8. Concomitant Medications
9. Treatment Stop Form

Clinic Laboratory Procedures and Physical Exam:

1. Four Glass Microscopy and Culture Test
2. Post Void Residual
3. Physical Examination
4. Semen Sample (collected only if participant has localized uropathogens at baseline. Participant will be scheduled 2-3 days following clinic visit for semen sample collection).

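### The screening order fixed by Sections 5.5 and 7.2 puts the rectal and prostate exam before the four-glass test, which may blur baseline cultures and white-cell counts

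*Protocol*

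**What the plan says.** Section 5.5 of the protocol turns the screening lists into a sequence. The data and procedures are "identified in Sections 7.2 and 7.3, in the order in which they will be obtained or undergone". The reason given is that "eligibility criteria checked by non-invasive methods precede those checked by more invasive methods", together with participant comfort and timeliness. Specimen quality is not among the reasons.

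In Section 7.2 (Screening Visit #1), item 5 is the physical examination: "This examination will include an abdominal exam, external genital exam, rectal exam, prostate exam, and perineal exam". Item 6 follows: "Each participant will provide the research staff with three (3) urine specimens and an EPS (expressed prostatic secretion) specimen for analysis and culture". The collection method is the four-glass test. EPS and VB3 results, when available, "will be compared with the findings from the 1st voided urine" (VB1) and from the midstream urine (VB2). There is no second chance at a visit: "The FGT will be attempted one time only at each of Screening Visit #1 and at the six (6) week clinic visit".

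Some men skip item 5: "Participants enrolled in the CPC who have completed a physical examination within one (1) month of enrolling in the RCT, will not be asked" to have it repeated.

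Section 7.6 lists the week-6 laboratory procedures and physical exam with "Four Glass Microscopy and Culture Test" first, post-void residual second and physical examination third. Appendix F sets the order inside the test (VB1, VB2, massage for EPS, VB3) but does not say where a rectal or prostate exam falls relative to it.

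**The concern.** The four-glass test separates what is in the urethra and bladder from what comes out of the prostate. It does so by collecting VB1 and VB2 before the prostate is manipulated. A rule that has the prostate palpated first works against that logic. Fluid expressed during the exam could be washed into VB1, and less might remain for EPS and VB3.

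The data at stake are secondary and mechanistic:

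- White cells in EPS are the laboratory measure named in Section 2.3.2.
- Change in four-glass white-cell counts is among the endpoints that Section 10.3.2 says may be compared between groups.
- Section 3.3 plans to relate response to ciprofloxacin to bacterial growth in the prostate or urine.
- Section 7.3 requires a man who gives no semen sample to have provided EPS or VB3 at Screening Visit #1, so yield at that visit has a practical consequence.

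**Working it through.** No power, alpha or sample-size figure is involved, and the plan gives no figure to reproduce. The check sets the texts side by side.

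**Order at each visit**

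| Place | Rectal and prostate exam | Four-glass test | Is the list an order of performance? |
|---|---|---|---|
| 7.2, Screening Visit #1 | item 5 | item 6 | Yes, by 5.5 |
| 7.6, week 6 | item 3 | item 1 | Not stated; 5.5 covers only 7.2 and 7.3 |
| Appendix C, forms schedule | row above the four-glass rows | rows below the exam | No; it schedules forms for both visits |
| Appendix F | not placed | VB1, VB2, massage, VB3 | Only within the test |

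1. Sections 5.5 and 7.2 together put the exam before VB1 and VB2 at screening.
2. Nothing in 7.2, 7.6 or Appendix F overrides this by requiring VB1 and VB2 to come first, or by saying that the prostate exam is done at the massage step.
3. The waiver in 7.2 means that some cohort participants give their baseline specimens with no exam beforehand at that visit, so the literal text produces two baseline conditions.
4. The 7.6 list differs from the 7.2 list. Without a sentence fixing its order, this is a mismatch in listing.

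**Why the size cannot be estimated**

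Let C be the bacterial count in prostatic fluid (CFU/mL), r the volume (mL) left in the urethra by the exam, and m the volume left by the massage. Appendix F gives 10 mL as the nominal VB1 and VB3 volume. Ignoring other sources of bacteria:

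- VB1 count = C × r / 10
- VB3 count = C × m / 10
- VB3:VB1 ratio = m / r

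C, r and m are not in the documents. As assumptions only, take r = 0.01 to 0.05 mL:

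- C = 10,000: VB1 = 10,000 × 0.01 / 10 = 10, up to 10,000 × 0.05 / 10 = 50 CFU/mL. That is 1 to 5 colonies on the 0.1 mL plate.
- C = 100,000: VB1 = 100 to 500 CFU/mL, or 10 to 50 colonies.

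The contrast between VB3 and VB1 depends only on m / r. If the exam leaves as much fluid as the massage, the ratio is 1. If the massage leaves ten times as much, it is 10. With r = 0 there is no effect. The answer is therefore set by the assumption.

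**EPS yield**

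Appendix F uses 5 microlitres of EPS for microscopy and 10 for culture. Together that is 15 microlitres, or 15/50 = 0.3 of a drop at its 50-microlitre conversion. Loss of volume prevents these two measurements only in men who yield almost nothing, and it does not by itself change a count made on a fixed 5-microlitre aliquot.

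**The case against.** The strongest reply is that this is a drafting matter with no demonstrated harm. Several parts of that reply stand.

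- **Contamination is not established.** A reader might infer that pre-massage urine is contaminated at baseline. No text says that a prostate exam expresses fluid, and Appendix F treats massage as its own step. Only a risk can be claimed.
- **A reversed procedure at week 6 is not established.** A reader might infer that part of the change from baseline is procedural. Section 5.5 does not govern 7.6, the 7.6 list groups laboratory procedures ahead of the exam, and Appendix C has the exam above the four-glass rows for both visits. List position alone does not show conduct.
- **Selection for the week-6 semen sample is not shown to be affected.** Section 7.6 refers to localized uropathogens at baseline, but the semen procedure in Appendix F ties the sample to baseline visit #2, when the four-glass test is not done.
- **Loss of localization is not a defined outcome.** The protocol states no VB3:VB1 cutoff. The ciprofloxacin question in 3.3 uses bacterial growth, and prostatic organisms found in VB1 would still count as growth. A baseline semen culture is also available for men who provide one.
- **Eligibility is not visibly at risk.** The urinary infection deferral in 4.1.3 uses more than 100,000 CFU/mL, far above the 10 to 500 CFU/mL illustrated above.

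The Manual of Procedures, which is not at hand, may also settle the order. That does not cure the protocol: its only explicit rule on sequence puts the exam first, and a manual that says otherwise would contradict it.

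**Conclusion.** The point holds as a defect in the stated order. Sections 5.5 and 7.2, read together, direct sites to palpate the prostate before collecting specimens whose value lies in being taken beforehand, in a test that is not repeated at that visit. The justification in 5.5 does not consider this.

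The possible effect is noise and misclassification in baseline four-glass cultures and white-cell counts, and so in change scores built on them. It also includes a difference in sampling conditions between men who have the exam and cohort participants who are exempt. The baseline specimens precede randomization, so an error in them cannot depend on assigned arm. This is not a source of between-arm bias. The primary endpoint is the NIH-CPSI change, which does not use the four-glass test.

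The conclusion rests on two assumptions: that sites follow 5.5 literally, and that a prostate exam can express some fluid. The documents do not test either one, and they do not support a numerical size. The correction is worth making because it costs almost nothing.

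**What to change.** In Section 7.2, list the four-glass test before the rectal and prostate exam, or state that the prostate exam is done at the massage step, after VB1 and VB2. In Section 5.5, add specimen integrity to the reasons for the order. Reconcile 5.5, 7.2, 7.6 and Appendix F so that one explicit sequence, with VB1 and VB2 collected before any rectal or prostate exam, applies at Screening Visit #1 and at week 6. Carry the same sequence into the Manual of Procedures.

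The cost is a few lines of wording. No visit, procedure or participant burden is added, and the sample size and primary analysis do not change.

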5.6 Informed Consent

Each clinical center will prepare an informed consent form following the guidelines of their local Institutional Review Board and applicable regulations for Informed Consent. The form will, at a minimum, contain a description of the potential risks, benefits, expense to the subject, and alternative treatment. The basic elements of the proposed informed consent are in **Appendix B**.

If the participant expresses interest in participating, he will be asked to sign and date the informed consent form. This form will provide consent for both the screening procedures and the follow-up procedures. Prior to signing the informed consent, the Research Coordinator will review the details of the consent form orally with the participant, and answer any questions that the participant has concerning participation in the RCT. The original signed consent form will be kept in the participant study file at the clinical center, while a copy of the signed consent form will be given to the participant.

6 TREATMENT PROCEDURES

Participants meeting all eligibility criteria will be randomized electronically to one of the four treatment arms. Each participant will receive a 6 (six)-week supply of tablets containing ciprofloxacin (CIPRO®) (or its matching placebo), and a 6 (six)-week supply of capsules containing tamsulosin hydrochloride (FLOMAX®) (or its matching placebo). The study medications will be provided in tamper evident sealed bottles, and will be labeled according to regulatory requirement per Code of Federal Regulations (CFR), Title 21, Part 312.6.

The Research Coordinator will provide explicit instructions to the participant at the time of randomization and dispensing of study drugs. The participant will be instructed that if at any time he should miss a daily dose, he should take the next dose at the usual time. The participant may not “double-up” a dose. The participant will be instructed to save the containers, even if they are empty, and return all study medications at each follow-up visit, to assist the study in compliance monitoring.

6.1 Ciprofloxacin (CIPRO®)

6.1.1 *Dosing Schedule*

The prescribed dose for ciprofloxacin (CIPRO®) is 500 mg twice a day (BID). The preferred time for dosing of ciprofloxacin is two hours after meals. Ciprofloxacin can be taken with or between meals. The drug should not be taken with milk or yogurt alone, however, because dairy products can decrease the absorption of ciprofloxacin. In addition, the use of antacids containing magnesium, aluminum or calcium and supplements containing iron or zinc can decrease the absorption of ciprofloxacin and should be avoided while taking the drug.

6.1.2 *Drug Manufacturing and Packaging*

Ciprofloxacin (CIPRO®) is manufactured by Bayer Corporation (West Haven, CT). Bayer Corporation will supply Ciprofloxacin (Cipro®) directly to the University of Pennsylvania Investigational Drug Service (IDS).

6.1.3 *Placebo for Ciprofloxacin*

The placebo tablets which are manufactured by Bayer Corporation, and are identical to Ciprofloxacin (Cipro®) tablets, will be shipped directly to the University of Pennsylvania Investigational Drug Service and will be taken on the same twice a day schedule (BID). Placebo for Ciprofloxacin (Cipro®) will be packaged and labeled identically to Cipro® tablets.

6.2 Tamsulosin Hydrochloride (FLOMAX®)

6.2.1 *Dosing Schedule*

The dose of tamsulosin hydrochloride (FLOMAX®) for this study is 0.4 mg daily, which is taken once a day (OD), 30 minutes following a meal. This dose is presently approved in the United States for the treatment of urinary symptoms related to benign prostatic hyperplasia. No dose titration is required.

6.2.2 *Drug Manufacturing and Packaging*

Tamsulosin hydrochloride (FLOMAX®) is manufactured by Yamanouchi Pharmaceuticals Co., Ltd. (Tokyo, Japan) and is distributed by Boehringer Ingelheim Pharmaceuticals, Inc.. Boehringer Ingelheim Pharmaceuticals, Inc. will supply Tamsulosin hydrochloride (FLOMAX®) directly to the University of Pennsylvania Investigational Drug Service.

6.2.3 *Placebo for Tamsulosin Hydrochloride (FLOMAX®)*

The placebo tablets which are manufactured by Yamanouchi Pharmaceuticals Co., Ltd. (Tokyo, Japan) and is distributed by Boehringer Ingelheim Pharmaceuticals, Inc., and are identical to tamsulosin hydrochloride (FLOMAX®) capsules, will be shipped directly to the University of Pennsylvania IDS and will be taken on the same once a day schedule (OD). Placebo for tamsulosin hydrochloride (FLOMAX®) will be packaged and labeled identically to (FLOMAX®) capsules.

6.3 Concomitant Medications

6.3.1 *Exclusionary Medications*

Participants will be monitored at each clinic and phone visit as to their use of over the counter and prescription medications. During the course of the study, the participant **MAY NOT** initiate or otherwise consume any of the following medications:

1. Tamulosin hydrochloride (FLOMAX®) other than study drug.
2. Ciprofloxacin (CIPRO®) other than study medication.
3. Terazosin HCL (Hytrin®) or doxazosin mesylate (Cardura®).
4. Antimicrobial agents.
5. Finasteride (Proscar®), or other 5-alpha reductase inhibitors, unless taking at baseline. (Note: If the participant is taking one of these medications at baseline, he should continue taking these for the duration of the study.)
6. Warfarin (Coumadin®).
7. Phenytoin (Dilantin®).
8. Probenecid (Benemid®).
9. Antacids.
10. Zinc Supplements.
11. Bioflavonoids (i.e. Quercetin).

